7.2 AGGREGATE RESULTS14
7.3 PROFESSIONAL REPORTING15

8. BIBLIOGRAPHY15

Promoting Follow-Up Care Self-Management for Adolescent and Young Adult (AYA) Childhood Cancer Survivors

[name], MPH

LIST OF ABBREVIATIONS

AYA	Adolescent and Young Adult
CINJ	Cancer Institute of New Jersey
LITE	Long-term, Information, Treatment effects, and Evaluation program
IRB	Institutional Review Board
NCI	National Cancer Institute
NIH	National Institutes of Health
PI	Principal Investigator
CCSS	Childhood Cancer Survivor Study

Promoting Follow-Up Care Self-Management for Adolescent and Young Adult (AYA) Childhood Cancer Survivors

[name], MPH

1. Purpose/Specific Objectives

Childhood cancer survivors are a growing population in the US (currently over 379,000).⁶ Unfortunately, these survivors are at risk for adverse health late effects from treatment such as cardiovascular disease and premature mortality.⁷⁻¹⁰ Survivors require lifelong follow-up care to identify, monitor, and treat medical and psychosocial late effects stemming from their cancer, its treatment, and lifestyle factors.¹¹ However, over 70% of childhood cancer survivors do not obtain specific risk-based follow-up care.¹² Adolescent and young adult (AYA) survivors of pediatric cancers are particularly vulnerable to lapses in follow-up care due to ineffective transitions from parent-guided management to self-management of care.^{11,13}

The transition from parent-guided management to self-management of long-term follow-up care involves assuming primary responsibility for tasks such as managing health records, making appointments, filling and taking prescriptions, and understanding late effects monitoring and cancer screening needs. It occurs during a critical developmental period when AYAs may be unaware or fail to recognize their health risks and need for regular follow-up.¹¹ Barriers to successful transition include survivors' lack of knowledge of their diagnosis and treatment, cancer-related anxiety and other emotional concerns, and failure or inability to assume personal responsibility for health.¹³⁻¹⁵

A survivor-focused intervention is likely to have the greatest impact on health outcomes because giving AYA survivors the knowledge, skills, support, and self-efficacy to manage their follow-up care will apply to any setting (i.e., cancer center or community-based primary care). This project takes an innovative approach to improving AYA survivors' self-management of long-term follow-up care through adaptation of an evidence-based problem-solving skills training (PSST) intervention and the addition of peer mentors to facilitate completion of the intervention. PSST has been shown to improve problem-solving skills in other cancer contexts,³⁻⁵ and we will adapt the content of the program to address the needs of AYA cancer survivors using patient, parent, and provider input. We anticipate that the adapted program will focus on improving disease knowledge, health motivation, problem-solving skills, stress management, and communication with caregivers and providers, all of which are important constructs to promote transition readiness as outlined in the Social-Ecological Model of AYA Readiness for Transition (SMART).¹ Peer mentors have been suggested as an innovative approach to support healthcare transitions,⁶ and many AYA survivors express a supportive care need to connect with other young adult survivors and seek advice from others who "get it."^{7,8}

The goal of this project is to develop and evaluate a peer mentoring self-management intervention to improve self-management skills for AYA survivors. We will evaluate feasibility (i.e., enrollment, retention, satisfaction with the program) and preliminary efficacy (i.e., changes in survivors' healthcare self-management skills, readiness to transition, and cancer-related anxiety). In Phase 1, we will use AYA survivor, parent, and provider interviews to adapt an evidence-based problem-solving skills training program to promote AYA self-management of care. We will recruit and train peer mentors to implement the PSST intervention. In Phase 2, we will conduct a pilot test of the program with 40 young adult survivors ages 18-25 years transitioning to self-management of follow-up care.

1.1 Objectives/Hypotheses

Promoting Follow-Up Care Self-Management for Adolescent and Young Adult (AYA) Childhood Cancer Survivors

[name], MPH

Aim 1: Adapt PSST with peer mentoring to improve AYA self-management of long-term follow-up care.

Qualitative research with AYA cancer survivors, parents, and healthcare providers will be conducted to adapt an evidence-based problem-solving skills training (PSST) program to address the needs of AYA survivors.

Aim 2: Evaluate the feasibility of the self-management + peer mentoring program in a pilot RCT.

We will examine feasibility through study enrollment rates, retention rates, adherence to the intervention, reasons for study drop out, and patient and mentor satisfaction with the program.

Hypothesis 1: Based on literature, we expect enrollment >50% of eligible patients and retention >75%.

Hypothesis 2: We expect patients enrolled in the mentor program to complete >75% of intervention sessions

Aim 3: Assess preliminary outcomes of the peer mentoring program.

Hypothesis 3: Participants in the mentor group will demonstrate improvement in self-management skills, transition readiness, and anxiety.

2. Background and Significance

The transition to adult self-management of health care is often ineffectively managed by AYAs.

Ineffective transition to adult self-management of care results in inadequate follow-up care and potential health problems. Although it is recommended that childhood cancer survivors obtain long-term follow-up care tailored to address the risks of their cancer, treatment, and lifestyle (called “risk-based follow-up care”), over 70% of young adult childhood cancer survivors do not obtain such care.^{9,10} Results from the largest cohort study of childhood cancer survivors, the Childhood Cancer Survivor Study (CCSS), show that even survivors at greatest risk for late effects demonstrate low rates of cancer screening.^{2,10,11} The transition to adulthood is a particularly challenging time when many AYAs are lost to follow-up.^{12,13} This is both a personal medical risk because late effects may go undetected or be misdiagnosed or mistreated, and a societal risk because lack of monitoring can lead to increased healthcare utilization and costs that may have been preventable. Barriers to adult-oriented health care transition for AYA survivors include survivor-related factors, such as inadequate knowledge of their cancer history and treatment, complex medical conditions, anxiety, and difficulty assuming personal responsibility for health.^{7,8,12,14,15} These survivor-related factors call for a survivor-focused intervention.

Theoretically-driven interventions to improve self-management of care are needed.

Promoting Follow-Up Care Self-Management for Adolescent and Young Adult (AYA) Childhood Cancer Survivors

[name], MPH

Although there is attention to AYA transition in the literature, a lack of transition-related theoretical frameworks has hindered the development and evaluation of targeted interventions to promote self-management of care.¹ The Social-Ecological Model of AYA Readiness for Transition (SMART)¹ proposes that there are modifiable factors that interact to promote AYA readiness for transition (Figure 1). Transition readiness refers to the capacity of the AYA and his/her support network to prepare for and complete the process of moving to adult-oriented care.¹ Factors related to transition readiness include knowledge of health history, risks, and needs; self-management skills and self-efficacy for managing care; beliefs and expectations regarding the transition process or adult-oriented care (such as belief that adult provider will not understand patient's needs); goals related to health transition; relationships with parents and providers; and psychosocial functioning of patients, parents, and providers (such as anxiety about the transition process or future health).¹ Problem-solving skills training (PSST) is a generic, cognitive-behavioral intervention that can be readily adapted to target these constructs. For example, PSST can be used to help AYAs set transition and self-management goals, explore beliefs/expectations related to the goals or barriers to such goals, manage stress, and promote self-efficacy by breaking down large goals into small, achievable steps. We chose PSST as an intervention because it empowers individuals to improve self-management skills, which include maintaining health records, making appointments, filling and taking prescriptions, and understanding health risks and monitoring needs. PSST also has a strong evidence base and has been shown to be effective for increasing problem-solving skills for parents who are managing a child's cancer treatment.³⁻⁵ We will use Phase 1 of this project to explore strategies for adapting PSST to address many of the modifiable components of the SMART model, including knowledge and communication with parents and providers.

[figure not shown]

Figure 1. SMART model^{1,2}

Peer mentoring meets a unique need for AYA childhood cancer survivors.

Qualitative and quantitative studies suggest that AYA survivors want to discuss their medical care needs with other AYA survivors.^{7,8,16,17} Although peer mentoring has been recommended as an innovative approach to facilitate health care transitions for AYAs,⁶ the only published intervention utilizing this approach for survivors is a peer-delivered counseling intervention for smoking cessation among adult childhood cancer survivors from the CCSS.¹⁸ Childhood cancer survivors who received the peer-delivered telephone counseling intervention were twice as likely to quit smoking as survivors who received the self-help print intervention, providing evidence of effectiveness of peer-to-peer programs for health behavior change in this population.¹⁸

Promoting Follow-Up Care Self-Management for Adolescent and Young Adult (AYA) Childhood Cancer Survivors

[name], MPH

Peer mentoring programs delivered using technology can be implemented across a variety of settings.

The Adolescent and Young Adult Oncology Progress Review Group (AYAO PRG) recommended the development of standardized peer-to-peer programs as a strategy for supporting the psychosocial needs of AYA cancer patients and survivors.¹⁹ The AYAO PRG suggested that efficacious programs be disseminated by partnering with cancer centers, oncology professional societies, and community-based support groups that work with AYA survivors. By partnering with various organizations, peer mentoring programs can be initiated and maintained with minimal health care system support. Peer-to-peer programs are also likely to be relatively low cost, as demonstrated by the peer counseling smoking cessation intervention for childhood cancer survivors, which has recently been translated to a web-based intervention.^{18,20} The use of technology to deliver skills-building modules and peer mentoring aligns with AYAs' preferences for technology, with 85% of young adults 18-29 owning smartphones.²¹ It also sets up the program for dissemination. Finally, since many childhood cancer survivors participate in volunteer activities and informal peer-to-peer outreach is commonly offered to cancer patients,¹⁸ sustaining a peer-to-peer program on a large scale is plausible.

3. Research Design and Methods

This research will be conducted in two phases. In Phase 1, we will use provider, survivor, and caregiver interviews to adapt PSST to focus on AYA self-management of care. In Phase 2, we will conduct a pilot test of the program with 40 young adult survivors ages 18-25 years and 20 peer mentors.

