3.4 Subject Selection and Enrollment Considerations

3.5.1 Inclusion Criteria

Phase 1:

Patient eligibility includes:

- (1) age 18-25
- (2) at least 1.5 years from treatment (which is a typical time for preparation to transfer to long-term follow-up care)

Parent eligibility includes:

- (1) caregiver of a pediatric cancer survivor age 18-25 who was primary caregiver at diagnosis
- (2) patient is at least 1.5 years from treatment

Provider eligibility:

- (1) health professional who works with childhood cancer survivors ages 18 to 25

Phase 2:

Peer mentor eligibility includes:

- (1) age 21-29
- (2) at least 1.5 years from treatment
- (3) self-reported primary responsibility for care and “complete readiness” using the Readiness for Transition Questionnaire²³

Patient eligibility includes:

- (1) age 18-25
- (2) at least 1.5 years from treatment
- (3) currently does not independently self-manage follow-up care according to self-report (i.e., reports low readiness to assume total responsibility for care [score of 1 or 2 out of 4 on overall readiness item OR scores <3 on any of the 10-item responsibility scale) using the Readiness for Transition Questionnaire²³)

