3.5.2 Exclusion Criteria

Phase 1:

Patient exclusion criteria includes:

- (1) physician- or self-reported cognitive delay or impairment that would prevent self-management of healthcare

Parent exclusion criteria includes:

- (1) patient has physician- or caregiver-reported cognitive delay or impairment that would prevent self-management of healthcare

Promoting Follow-Up Care Self-Management for Adolescent and Young Adult (AYA) Childhood Cancer Survivors

[name], MPH

No provider exclusion criteria

Phase 2:

Patient exclusion criteria includes:

- (1) physician- or self-reported cognitive delay or impairment that would prevent self-management of healthcare
- (2) patients with cancer diagnoses that are not typically considered pediatric cancer, including basal and squamous cell skin cancer, breast, colorectal, lung, melanoma, merkel cell skin cancer, ovarian, testicular, kidney cancer diagnosed at age >17, and nasopharyngeal diagnosed at age > 17.

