Phase 2: Peer mentors will be recruited via advertisements in the CINJ LITE clinic and newsletter, AYA cancer support groups, and online forums/social media, such as stupidcancer.org. Following the Children's Oncology Group's approach to recruiting patient advocates, potential mentors will complete an application including two letters of recommendation. The PI or study staff will interview candidates to evaluate interpersonal skills, level of commitment to the program, and counseling or related experience. Participants for the randomized trial will be recruited using the New Jersey State Cancer Registry (NJSCR). All participant information and surveillance data from the NJSCR is collected and maintained by the NJSCR following Standard Operating Procedures (see IRB#Pro20140000992 NJSCR SEER Data Repository). Patient contact procedures, tracking, and data release also follows NJSCR Standard Operating Procedures. Per Standard Operating Procedures, NJSCR staff will contact the physician of record for eligible cases to notify the physician about the study and that staff will be contacting the patient. An introductory letter and flyer will be mailed to potential participants. NJSCR staff will make follow-up phone calls to provide additional information and, for patients who express interest in participating, to obtain permission

Promoting Follow-Up Care Self-Management for Adolescent and Young Adult (AYA) Childhood Cancer Survivors

[name], MPH

to send their contact information to [name] study staff, who will then contact the patient for further details and discussion of consent.

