3.5.4 Consent Procedures

The study will be explained to the potential participant by the Principal Investigator or trained study staff via phone. The PI or study staff will review essential elements of consent and answer any questions. Interested and eligible participants will be emailed a link to an online consent form prior to starting the program. To consent, potential participants will be instructed to click "submit the form" button in order to consent.

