4.1 Independent Variables or Interventions

Phase 1: Semi-structured interview guides will be used to conduct interviews. The goal of the interviews is to understand patient, parent, and provider perspectives on the challenges faced by AYAs in managing their health care and on how PSST materials can be adapted to address the challenges of self-management of care.

Phase 2: Independent variables include demographics (age, gender, socioeconomic status, education, employment status, living at home or independently) and cancer diagnosis and treatment history (i.e., diagnosis, time since treatment completion, types of treatment received). Diagnosis and date of diagnosis will be obtained from NJSCR records and the remaining information from self-report.

Peer Mentoring Intervention. Based on initial interviews and feedback on the PSST intervention, we identified five major themes to be addressed in our program. The intervention will include two components: (1) online self-management educational modules using the Rutgers Canvas online course platform and (2) weekly video-conference calls on Doxy.me between the peer mentor and participant. Table 1 shows the content of the five online modules based on preliminary work. Participants are expected to complete one module per week in addition to a call with their mentors. Each module takes approximately 30 minutes to complete and ends with a personalized assignment for the participant to complete on his/her own (e.g., obtain survivorship care plan, make an appointment, practice communication skills).

Participants will be matched with a peer mentor of the same sex and cancer type to the extent possible.^{24,25} The objectives of the first mentor call are to build rapport, exchange stories regarding current long-term follow-up care, and identify the participant's self-management

Promoting Follow-Up Care Self-Management for Adolescent and Young Adult (AYA) Childhood Cancer Survivors

[name], MPH

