4.2 Dependent Variables or Outcome Measures

Phase 1: The primary outcome measure is qualitative interview data. Interviews will be transcribed for analysis (see Data Handling and Statistical Analysis section for details). Participants will also be asked to complete the questionnaires selected for Phase 2 and provide feedback to the study staff regarding how well the questionnaires capture self-management of survivorship care.

Phase 2: The following standardized measures will be administered at baseline and immediately post-intervention (~6 weeks), except where noted:

Transition readiness. The Readiness for Transition Questionnaire – Survivor Version (RTQ)²³ is a 22-item scale evaluating transition readiness for cancer survivors. Respondents are asked to rate the degree to which they are responsible for various aspects of their health care, such as knowing their survivorship care plan, scheduling visits, and filling prescriptions. They are separately asked to rate the degree to which their parents are responsible for managing the same aspects of their care. Two questions ask about the survivors' overall perception of their readiness to transfer to an adult-approach to health care. The RTQ has demonstrated adequate reliability.²³

The Transition Readiness Inventory (TRI), developed using the SMART framework,²⁸ is a comprehensive measure of multiple components of transition readiness. While the RTQ focuses on responsibility for behaviors, the TRI focuses on behaviors *and knowledge, attitudes, and beliefs*. Specifically, the TRI yields a total score and provides scales for the following targets of our intervention: knowledge, self-management skills, self-efficacy for managing care, goals/motivation, and communication with family and providers around survivorship care. The TRI has shown adequate reliability and content validity,^{28,29} and evidence of predictive validity of engagement in adult healthcare.²⁹ We will utilize the total TRI score.

Anxiety. PROMIS Depression and PROMIS Anxiety measures are validated 8-item measures of depressive symptoms and anxiety. We will examine cancer-related anxiety using the Fear of Recurrence Scale,³⁰ which has been used with young adult survivors of childhood cancers.³¹ Finally, we will adapt items to examine anxiety related to healthcare transition and cancer late effects. We will also use the Cancer Related Worry Scale to assess participants' concerns related to their cancer past and future.

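### Does leaving the counting stage for eligible patients unstated, in the expectation that more than half enroll, call for a change to the plan?

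*Combined protocol and SAP*

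**What the plan says.** Section 1.1 (Aim 2, Hypothesis 1) sets the expectation: "Based on literature, we expect enrollment >50% of eligible patients and retention >75" per cent. Section 5 repeats it and says that descriptive analyses will evaluate it. Neither place gives a numerator, a denominator or a counting stage.

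The word eligible appears at two stages of Phase 2 recruitment:

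- Section 3.5.3, before any patient contact: "NJSCR staff will contact the physician of record for eligible cases". Letters and registry staff calls follow. The call gives information and serves, "for patients who express interest in participating, to obtain permission", to pass contact details to the study staff.
- Section 3.5.4, just before consent: "Interested and eligible participants will be emailed a link to an online consent form prior to starting the program".

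The Phase 2 criteria include low readiness on the Readiness for Transition Questionnaire (RTQ), meaning that the patient "currently does not independently self-manage follow-up care according to self-report" (section 3.5.1). They exclude "physician- or self-reported cognitive delay or impairment that would prevent self-management of healthcare" (section 3.5.2). On data sources, section 4.1 says: "Diagnosis and date of diagnosis will be obtained from NJSCR records and the remaining information from self-report". The RTQ is also an outcome measure, under the heading sentence in section 4.2: "The following standardized measures will be administered at baseline and immediately post-intervention (~6 weeks), except where noted".

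Section 3.3 plans 40 survivors and makes feasibility the primary objective. Section 5 plans a database for recruitment and tracking.

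**The concern.** Enrollment is one of three quantified feasibility expectations, and feasibility is what the pilot is for. A proportion needs a denominator, and the two uses of eligible describe different groups. The registry cannot know a patient's RTQ score, so its eligible cases are only provisionally eligible. The people called eligible at the consent step have already passed an interest filter, and no RTQ screen is described before that filter.

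Taken literally, the eligibility of people who decline or are never reached stays unknown. Enrolled divided by known eligible then leaves out eligible people lost earlier. It can show that 50% was missed, but taken alone it cannot show that 50% was met among all eligible patients. A reader planning a larger registry-recruited trial could mistake a high consent rate among interested people for high uptake in the population.

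**Working it through.** **1. What must come from the patient.** Of the criteria at issue, only the RTQ score clearly needs the patient's own report. Cognitive impairment may be reported by a physician, and the physician of record is contacted before the patient, although that contact is described only as notification. Section 4.1 lists time since treatment completion as self-reported, but it is giving sources for study variables. It does not say what the registry may use to select cases.

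**2. When the RTQ screen happens.** If it were first given at the baseline assessment, after consent, everyone found eligible would already have consented and the rate would be about 100% by construction. Section 3.5.4 rules this out, because the consent link goes only to people already found eligible. Section 4.2 schedules the RTQ as an outcome and does not forbid earlier use. Section 3.5.1 uses the same instrument to select peer mentors, so using it as a screen is natural. The sections are compatible; only the timing of the screen is unwritten.

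**3. The threshold.** The plan has no calculation to reproduce. The 50% is credited to literature and team experience, and the 40 is not derived from it. With 40 enrolled (section 3.3) and denominator D:

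40/D > 0.5 requires D < 80, so D ≤ 79. Check: 40/79 = 50.6%; 40/80 = 50.0%, which is not above 50%.

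**4. How far the observable rate can mislead.** Let K be the number known to be eligible (assumed values). The expectation holds among all eligible patients only if at most 79 − K eligible people went unscreened.

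| K | 40/K | 79 − K |
|---|---|---|
| 45 | 88.9% | 34 |
| 50 | 80.0% | 29 |
| 60 | 66.7% | 19 |
| 70 | 57.1% | 9 |

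Equivalently, the rate among all eligible patients is p × c. Here c is consent among screened-eligible people, and p is the share of eligible patients who are reached, interested and screened. Exceeding 50% needs p > 0.5/c: 50% when c = 100%, 56% when c = 90%, 63% when c = 80%, 71% when c = 70%.

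**5. What step counts recover.** With U people mailed but not screened, counting all or none of them as eligible gives bounds of 40/(K + U) and 40/K. Assumed examples:

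- K = 50, U = 150: 40/200 = 20.0% to 40/50 = 80.0%. The rate is 50% or lower once (80 − 50)/150 = 20% or more of the unscreened are eligible. The counts do not settle it.
- K = 50, U = 20: 40/70 = 57.1% to 80.0%. The expectation is met on either count.

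If no more than 79 registry cases yielded the 40, the expectation would be confirmed with no screening of decliners, because 40/79 already exceeds 50%. The expectation can therefore be confirmed on some counts. Whether it will be depends on counts that the documents do not give. The lower figure covers only people who were mailed; cases identified but never mailed lie outside it.

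**The case for a change.** The strongest case for a change is that timing matters. Step counts reported afterwards only bound the rate, because the eligibility of decliners cannot be recovered once they have gone. If the target is all eligible patients, the screening step has to be settled before recruitment. Naming the denominator costs a sentence, and a descriptive proportion needs a denominator as much as a tested one does.

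Part of this stands. The counting stage is unnamed, the timing of the RTQ screen is unstated, and a conditional consent rate should not be presented as population uptake.

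The rest does not carry a change. Eligible patients can fairly mean patients found eligible, which is how section 3.5.4 uses the word; on that meaning the rate is computable as the plan stands. Section 3.5.3 places contact, tracking and data release under registry operating procedures that are not in the documents, so a screen on the registry call is neither described nor excluded. Screening before interest, or screening decliners, would lengthen the call and need registry and IRB agreement. Decliners who agreed to answer would be a selected group, and people never reached would remain unknown. That is a debatable trade-off in a 40-person pilot.

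**Conclusion.** The omission is real but small: an unwritten definition for a descriptive expectation to which no test, error rate or progression rule is attached. An analyst would fill it from the planned tracking database by reporting numbers identified, mailed, reached, interested, screened, eligible and consented, and by saying which ratio is quoted. A reader could then form either rate and the bounds.

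The possible gap between the two rates can be wide (20% against 80% in one assumed example) or too small to alter the conclusion (57% against 80% in another). Only the 40 and the 50% come from the documents; every other count is an assumption, so no actual distortion is shown. The conclusion assumes that eligibility is settled before the consent link is sent, as section 3.5.4 says, and that recruitment counts are kept and reported. On that footing no change to the plan is needed.
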